16.7 Adjudication of Primary Endpoint

All rating sessions for MADRS-10 and C-SSRS will be recorded as audio files and reviewed by central master-raters with > 25 years of experience. Any MADRS-10 total score the differs by more than three points from the master-rater score will be deemed non-congruent. All non-congruent subject-visits from any site with > 10% non-congruent scores will be sent to an independent adjudicator, previously determined to have > 90% concordance with study master

raters on standardized training data. In the event of adjudication as above, the independent outside rater score shall be considered as the subject-visit primary study endpoint.

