Dosage, Route of Administration, and Schedule:	
On Day 1, eligible participants will be randomized to blinded NRX-101 or lurasidone and placebo capsules administered twice daily (BID).
 
Investigational product will be titrated over 2 days. In the case of randomization to NRX-101, the blinded investigational product will consist of daily doses of 700 mg DCS and 33 mg lurasidone and increasing the dose to 950 mg DCS and 66 mg lurasidone on second day. The total daily NRX-101 maintenance dose for Day 3 through Day 42 is 950 mg DCS and 66 mg lurasidone. In the event a patient experiences agitation or psychosis, a blinded up-titration is permitted. Similarly, a blinded step-down titration is allowed for somnolence. In order to maintain the blind, lurasidone/placebo capsules will be administered to ensure participants take the same number of capsules with each dose administration.
 
NRX-101 is supplied in capsules that contain 237.5 mg or 175 mg of DCS and a second capsule that contains 8.25 mg, 16.5 mg, or 33 mg of lurasidone. In order to maintain the blind, lurasidone/placebo capsules will be administered to ensure participants take the same number of capsules with each dose administration.
 
In the case of randomization to lurasidone, the blinded investigational product will start with doses of 33 mg lurasidone and increasing the dose to 66 mg. The total daily lurasidone maintenance dose for Day 3 through Day 42 is 66 mg.

Endpoint Adjudication	
All rating sessions for MADRS-10 and C-SSRS will be recorded as audio files and reviewed by central master-raters with >25 years' experience. Any MADRS-10 total score that differs by more than three points from the master-rater score will be deemed non-congruent. All non-congruent subject-visits from any site with >10% non-congruent scores will be sent to an independent adjudicator previously determined to have >90% concordance with study master raters on standardized training data. In the event of adjudication as above, the independent outside rater score shall be considered as the subject-visit primary study endpoint.

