## 17. ENDPOINTS

### 17.1 Efficacy

#### 17.1.1 Primary Efficacy Endpoint

The primary efficacy endpoint is the change from baseline in the total MADRS score as measured by psychometric raters assessed over 42 days post randomization by mixed-model repeated measures analysis.

The primary endpoint will be based on adjudicated results. All rating sessions for MADRS-10 and C-SSRS will be recorded as audio files and reviewed by central master-raters with  $> 25$  years of experience. Any MADRS-10 total score that differs by more than three points from the master-rater score will be deemed non-congruent. All non-congruent subject-visits from any site with  $>10\%$  non-congruent scores will be sent to an independent adjudicator, previously determined to have  $>90\%$  concordance with study master raters on standardized training data. In the event of adjudication as above, the independent outside rater score shall be considered as the subject-visit primary study endpoint.

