#### 19.4 Estimand Structure

Analyses will be conducted in accordance with ICH E9 (R1) analysis principles as summarized below.

Primary scientific question of interest	The primary study hypothesis is that treatment with NRX-101 is superior to lurasidone in improving symptoms of depression as measured by the MADRS over 6 weeks of treatment. The null hypothesis for the primary endpoint is the mean change from baseline of MADRS-10 for NRX-101 is the same as lurasidone while the alternative hypothesis is that the mean change from baseline of MADRS-10 is larger than the mean change from baseline of MADRS-10 for lurasidone. Baseline is defined as MADRS-10 score at Visit 2 (randomization).
Target population	The mITT population will be the primary analysis population. The mITT population is defined through appropriate inclusion/exclusion criteria as specified in the protocol and blinded BDRM decisions.
Treatment of interest	NRX-101
Outcome Variables	MADRS-10 (and C-SSRS) will be recorded as audio files and reviewed by central master-raters with any non-congruent subject-visits from any site with >10% non-congruent scores sent to a qualified independent adjudicator to be considered as the subject-visit primary study endpoint.
Summary Measure	The contrast-estimated MADRS-10 Week 6 MMRM will use all post-randomization data with LOCF in the mITT population excluding all outcomes after BDRM-approved exclusions. The model will include treatment and the following four baseline covariates in addition to baseline MADRS-10: (1) sex, (2) mood stabilizer use, (3) anti-psychotic use, and (4) evidence of suicide event in their lifetime. The model will include treatment group, study visit, the interaction between study visit and treatment group, baseline MADRS-10, and the four baseline covariates as fixed effects. An unstructured error structure will be assumed.
Intercurrent Events	A BDRM will adjudicate all intercurrent events which may redact outcomes after disqualifying events; these intercurrent events may represent major protocol deviations.

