## 20. STATISTICAL METHODOLOGY

### 20.1 General Methodology

The Mixed-Effect Model Repeated Measure (MMRM) will be the primary analysis for the primary efficacy endpoint (MADRS change from baseline); an unpaired t-test will be a secondary analysis. The proportional hazard model (PHREG) will be the primary analysis for time to event endpoints (time to remission, time to discontinuation); the unstratified log rank test will be a secondary analysis. The MMRM and PHREG models will all include treatment and the following four baseline covariates:

- sex
- mood stabilizer use
- anti-psychotic use
- evidence of suicide event in their lifetime.

All primary analyses will be in the mITT population as primary and repeated in the Per Protocol population if >5 percent are excluded.

All of the instruments used to measure SSIB or depression constitute serial continuous and ordinal outcomes that will be analyzed using MMRM with LOCF to account for missing data and early discontinuations. The models will include treatment group, study visit, the interaction between study visit and treatment group, the baseline level of the variable being analyzed, and the above four pre-defined baseline stratification factors as fixed effects. The primary endpoint change from baseline MADRS-10 will be analyzed using the MMRM model which will include baseline MADRS; treatment group; study visit; study visit\*treatment; sex, mood stabilizer use, anti-psychotic use, and evidence of suicide event in their lifetime as defined above. An unstructured error structure will be assumed.

SAS PROC MIXED will be used for continuous endpoints.

In addition, supportive analyses will be performed using multiple imputation which will be performed to address any missing data. The method of Little and Rubin will be used. The presentation of the results for the primary efficacy endpoints using the ITT population will be based on the observed data with multiple imputation for missing endpoint data using SAS PROC MI. Missing data will be imputed using MCMC imputation under the assumption of a missing at random using the mITT population. The SAS® procedure PROC MI will be used for the MCMC imputation of 25 complete data sets.

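### Adjudication replaces single visits, so one patient's change from baseline can mix two raters and carry avoidable measurement error

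*SAP*

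**What the plan says.** SAP 17.1.1 defines the primary endpoint as the "change from baseline in the total MADRS score as measured by psychometric raters assessed over 42 days post randomization". SAP 19.4 takes baseline from Visit 2, and SAP 20.1 fits an MMRM to the change with baseline MADRS as a covariate.

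The adjudication rule has three steps, each defined for a single visit:

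- **Flag.** A MADRS total that "differs by more than three points from the master-rater score will be deemed non-congruent" (SAP 17.1.1).
- **Refer.** "All non-congruent subject-visits from any site with > 10% non-congruent scores will be sent to an independent adjudicator" (Protocol 16.7).
- **Replace.** "the independent outside rater score shall be considered as the subject-visit primary study endpoint" (SAP 3, repeated in SAP 17.1.1). The estimand table in SAP 19.4 says the same: flagged visits are "sent to a qualified independent adjudicator to be considered as the subject-visit primary study endpoint".

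Neither document extends the replacement to the patient's other visits, requires both scores of a change to come from the same rater, or puts the source of the score into the model. Day 1 is itself a recorded rating session, so either end of a change can be replaced alone.

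**The concern.** If a site rater scores consistently high, that offset drops out of a raw difference as long as the same rater supplies both ends. Replace one end only, and the part of the offset left in the retained score goes into the patient's change. A score can be retained while up to three points from the master-rater, so a patient near the limit can easily have one visit kept and another replaced.

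The rule exists to improve the primary endpoint, and replacing visits one at a time gives up part of that gain. What is at stake is accuracy of individual change scores at sites over the 10% trigger. Two other outcomes could also be touched: remission (MADRS of 10 or less at the last two visits, SAP 17.1.4) and worsening (a rise of at least 5 points from the previous visit, SAP 20.4). The SAP does not say whether adjudicated totals feed these.

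**Working it through.** **1. The plan's own figure.** 8.85 / 13.4 = 0.660. A two-sample t-test with 37 per group and two-sided alpha 0.05 has power 79.98%, which reproduces the stated 80% (SAP 3 and 18.2).

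**2. An example that follows the rule.** Suppose the site scores 33 at Day 1 and 24 at Day 42, the master-rater scores 30 and 20, and the adjudicator agrees with the master-rater. Day 1 differs by 3 and is kept. Day 42 differs by 4 and is replaced.

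- Site scores only: 24 − 33 = −9
- Central scores only: 20 − 30 = −10
- The rule: 20 − 33 = −13

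**3. How often the ends are mixed.** Totals are whole numbers, so a flag needs a difference of at least 4. Write b for the site offset and s for the SD of site minus master-rater (both assumed). Ignoring the negligible lower tail here, p = P(Z > (3.5 − b)/s), and the chance that exactly one of Day 1 and Day 42 is flagged is 2p(1 − p).

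- b = 3, s = 1.5: p = P(Z > 0.333) = 0.369, and 2 × 0.369 × 0.631 = 0.466
- b = 4, s = 1.5: p = 0.631, again 0.466

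This treats visits as independent given the offset.

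**4. Size of the error in raw change.** Simulation of 400,000 patients at a site over the trigger. Assumed: site score = truth + offset + noise; master-rater and adjudicator = truth + noise with SD 0.7; scores rounded. RMS error of Day 42 minus Day 1:

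| Site offset | Site noise SD | Site scores untouched | Rule as written | Same source for a flagged patient |
|---|---|---|---|---|
| 2 | 1 | 1.47 | 1.52 | 1.26 |
| 3 | 1 | 1.47 | 2.03 | 1.11 |
| 4 | 1 | 1.47 | 2.32 | 1.07 |
| 3 | 1.5 | 2.16 | 2.03 | 1.28 |
| 4 | 1.5 | 2.16 | 2.17 | 1.13 |
| 3 | 2 | 2.85 | 2.05 | 1.44 |
| 4 | 2 | 2.86 | 2.06 | 1.21 |

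Mixed-rater changes occur in about 45 to 48% of patients at offsets 3 to 4, and in 20% at offset 2 with noise SD 1. With central noise SD 1 instead of 0.7, offsets 3 to 4 and site noise SD 1 to 2 give 2.2 to 2.6 under the rule and 1.4 to 1.7 with one source. In those runs the mean error among mixed patients is 1.8 to 3.2 points in absolute value, negative when Day 42 is replaced and positive when Day 1 is; it is 0.0 with one source. Over all patients the two kinds of mix balance to about 0.

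**5. The adjusted analysis.** With baseline as a covariate, modelling the change is the same as modelling Day 42 minus β times baseline, so the error that counts is e42 − β·e0. In the example, taking the central score as truth, site scores give 4 − 3β and the rule gives −3β. The two are equal in size at β = 4/6 = 0.67. At β = 1 the errors are 1 and 3 points; at β = 0.5 they are 2.5 and 1.5. The documents do not give β. RMS errors at site noise SD 1, central SD 0.7, as untouched / rule:

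| β | Offset 3 | Offset 4 |
|---|---|---|
| 1 | 1.47 / 2.03 | 1.47 / 2.32 |
| 0.75 | 1.50 / 1.85 | 1.64 / 2.07 |
| 0.5 | 1.90 / 1.81 | 2.31 / 1.91 |
| 0.25 | 2.49 / 1.93 | 3.19 / 1.87 |

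Across offsets 0 to 5, site noise SD 1 to 3 and β from 0.25 to 1, having the adjudicator score all of a flagged patient's visits matched or beat the rule in every setting.

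**6. Effect on the comparison.** Treating every patient as if at such a site, with an unadjusted t-test and central noise SD 1, power is 78.9 to 80.8% under the rule and 80.0 to 81.3% with one source. The largest gap is at offset 4, site noise SD 1: the SD of change is 13.585 against 13.409, and power 78.9% against 80.0%. A chance excess of 4 mixed patients in one arm, each off by 3 points the same way, would move that arm's mean by 4 × 3 / 37 = 0.32 points.

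**The case against.** The strongest reply is that the harm is small and may not be harm at all. A reader might infer that the rule makes the primary endpoint less accurate than leaving site scores alone. The documents do not support that. It holds for unadjusted change when site noise is low, but the primary model adjusts for baseline, where an offset cancels fully only at β = 1. At β = 0.5 or below, or with site noise SD of about 1.5 to 2 or more, the rule generally matches or beats untouched site scores. Nor can one assume that sites over the trigger have a steady offset: with no offset and site noise SD 2, about 10% of visits are flagged by noise alone.

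A reader might also infer a biased treatment effect. With blinded raters and 1:1 allocation, mixed-rater patients should fall alike in both arms, so no bias is expected.

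The plan has safeguards too: raters are trained and approved before enrollment (Protocol 17.1), retrained if reliability fails (Protocol Appendix 3), and unreliable MADRS scoring is a ground for exclusion from the per-protocol set (SAP 15). These limit the problem without removing the mixing.

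All of this stands. What it does not answer is that scoring a flagged patient from one source does at least as well as the rule whichever offset, noise level or slope applies, so the sponsor need not know them to choose it.

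**Conclusion.** The point holds as an avoidable loss of precision. As written, a change from baseline at a site over 10% non-congruence can mix two raters. At assumed offsets of 3 to 4 points and site noise SD 1 to 2, RMS error of the raw change is about 2.0 to 2.3 points, against 1.1 to 1.4 with one source; both ranges rise somewhat if the central raters are noisier. Sites at or below the trigger are unaffected. Against a between-patient SD of 13.4 the cost is about one point of power at most, with no expected bias. This is a cheap improvement that does not threaten the trial's conclusion.

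**What to change.** State in SAP 3, 17.1.1 and 19.4 that once any MADRS visit of a patient is adjudicated, that patient's Day 1 and all post-baseline scores come from one source. The master-rater scores are the simplest choice: every MADRS session is reviewed centrally, and the three-point test cannot be applied without a master-rater total for each. The alternative is to have the adjudicator score all of that patient's sessions.

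Pre-specify the primary MMRM on master-rater scores throughout as a sensitivity analysis. That also removes the between-patient difference in source, which matters when β is below 1 because patients with no flagged visit keep their site scores.

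The cost is SAP wording and one more model run, plus a few more recordings for the existing adjudicator if adjudicator scores are chosen. SAP 13 lets the SAP govern where it differs from the protocol, so the SAP text is enough.

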## **5. LIST OF ABBREVIATIONS**

Abbreviations	Full Terms
ACPC	Aminocyclopropanecarboxylic Acid
AE	Adverse Event
SSIB	Subacute Suicidal Ideation or Behavior
BARS	Barnes Akathisia Rating Scale
BDRM	Biostatistics Data Review Meeting
BID	Twice Daily
BMI	Body Mass Index
BPI	Bipolarity Index
BPRS(+)	Brief Psychiatric Rating Scale(+)
CFB	Change from Baseline
CFR	Code of Federal Regulations
CGI-SS	Clinical Global Impressions of Severity for Suicidality
CHF	Congestive Heart Failure
CHRT-C	Concise Health Risk Tracking-Clinician
CHRT-SR	Concise Health Risk Tracking-Self Report
CLIA	Clinical Laboratory Improvement Amendments
Cmax	Maximum Concentration
CNS	Central Nervous System
CP	Conditional Power
CRO	Contract Research Organization
C-SSRS	Columbia Suicide Severity Rating Scale
DCS	D-cycloserine
DSM-5	Diagnostic and Statistical Manual of Mental Disorders Fifth Edition
ECG	Electrocardiogram
eCRF	Electronic Case Report Form
eGFR	Estimated Glomerular Filtration Rate
ECT	Electroconvulsive Therapy
FDA	Food and Drug Administration
GCP	Good Clinical Practice
HbA1c	Glycosylated Hemoglobin
HDPE	High Density Polyethylene
HIPAA	Health Insurance Portability and Accountability Act
HPMC	Hydroxymethylcellulose
ICH	International Conference on Harmonisation
ITT	Intent-to-Treat
IUD	Intrauterine Device
IWRS	Interactive Web Response System
Lurasidone	Lurasidone HCl
LOCF	Last Observation Carried Forward
MADRS	Montgomery Asberg Depression Rating Scale
MDD	Major Depressive Disorder
MMRM	Mixed Model Repeated Measures
NMDAR	N-methyl-D-aspartate Receptor

NOS	Not Otherwise Specified
OSFED	Other Specified Eating Disorder
PCP	Phencyclidine
PRISE	Patient Rated Inventory of Side Effects
QTcF	Fridericia's Correction Formula
SAE	Serious Adverse Event
SAP	Statistical Analysis Plan
SIBAT	Suicide Ideation and Behavior Assessment Tool
SNRI	Serotonin and Norepinephrine Reuptake Inhibitors
SOP	Standard Operating Procedure
SSRI	Selective Serotonin Reuptake Inhibitor
TB	Tuberculosis
TeCA	Tetracyclic Antidepressant
TTF	Time to Treatment Failure

## 6. INTRODUCTION

### 6.1 Suicidal Ideation and Behavior in Bipolar Disorder

Bipolar Disorder (formerly known as manic depressive disorder) is a well-established psychiatric diagnosis, with a prevalence of about 2.6% in the United States (approximately 8.5 million people) (Kessler et al., 2005). The risk of subacute suicidal ideation or behavior (SSIB) is uniquely high in patients during bipolar depressive episodes, compared to those with major depressive disorder (MDD), thought disorders, and personality disorders. Lifetime suicide behavior occurs in 25% to 56% of people with bipolar disorder (Nierenberg et al., 2001). About 40% of the nearly 50,000 annual deaths from suicide in the United States are associated with bipolar disorder (Mahli et al., 2015). The overall rate of death by suicide among patients with bipolar disorder is 164 per 100,000 person years, compared to about 14 per 100,000 person years for the general population. Those who have attempted suicide are 2.3 times more likely to die by suicide compared to those without a suicide attempt (Coryell et al., 2016). Thus, bipolar depression with suicidal ideation has uniquely lethal clinical characteristics (Pompili, et al., 2013).

### 6.2 Current Treatment Options

Despite its lethal characteristics, there is no approved pharmacologic treatment for patients with bipolar depression and suicidal ideation. Electroconvulsive therapy (ECT), often combined with inpatient psychiatric care, remains the only Food and Drug Administration (FDA)-approved treatment for patients with acute suicidal ideation in bipolar depression, despite ECT's well-documented side effects that include memory loss and confusion, along with its high cost. However, the toxicity of ECT is such that it is less likely to be used in patients with subacute levels of suicidal ideation and no oral medication has been shown to reduce suicidal ideation in patients with depression in general or bipolar depression in specific. Physicians are increasingly cautious about the use of selective serotonin release inhibitors (SSRIs), particularly in patients with suicidal ideation because of evidence that SSRIs and other antidepressants may actually increase the risk of suicidal ideation, particularly in younger patients (Stone et al., 2009). This evidence has resulted in an FDA warning on the label of current antidepressants. Moreover, it seems clear that antidepressants do not decrease SSIB in proportion to their mitigating effect on symptoms of depression.

In recent years, several combined D2/5-HT2A antagonists have shown efficacy in treating bipolar depression (olanzapine/fluoxetine combination, quetiapine, and lurasidone) with treatment guidelines endorsing common use as first-line standard of care treatment in acute bipolar depression. While these medications are effective at reducing overall symptoms of depression, they do not specifically reduce suicidal ideation, as shown in recent clinical trials of lurasidone (Loebel et al., 2014a; Loebel et al., 2014b). Moreover, in these two studies, individuals with active suicidal ideation (Montgomery Asberg Depression Rating Scale [MADRS] item 10  $\geq$  4) were specifically excluded because of concerns regarding the possibility of exacerbating suicidality with these medications. Similarly, acutely suicidal patients are routinely excluded from clinical trials of other experimental anti-depressive agents. Thus, bipolar depression with suicidal ideation

[figure not shown]
represents a major unmet medical need that must frequently be treated with voluntary or involuntary hospitalization under highly supervised conditions and ECT.

### **6.3 Clinical Experience with DCS**

Antidepressant effects of high-dose DCS were first noted in the late 1950s, when it was introduced as a treatment for tuberculosis (TB). Several clinicians noted dramatic improvement in patients' depressive symptoms, leading to suggestions of DCS' potential psychotropic effects. These effects were subsequently confirmed in small-scale clinical studies (Crane, 1959 and 1961). The mechanism of action was unknown at the time, and the finding was not pursued. The interaction of DCS with the NMDAR was first demonstrated in 1989 (Hood et al., 1989), leading to some interest in NMDAR blockers as potential antidepressant treatments (Trullas and Skolnick, 1990; Skolnick et al., 1996). For example, both DCS and the related compound aminocyclopropanecarboxylic acid (ACPC) were shown to be active in mice, using the forced swim test for depression (Lopes et al., 1997). To the best of our knowledge, no clinical antidepressant research programs targeting the NMDA receptor were initiated at that time.

Interest in the potential clinical use of DCS as an antidepressant agent was renewed following Berman's fortuitous observation of ketamine's rapid antidepressant effect (Berman et al., 2000). An initial study performed with DCS at a dose of 250 mg/day did not show therapeutic effects, but it did demonstrate a relative lack of psychotomimetic side effect when DCS was combined with concurrent antidepressant treatment (Heresco-Levy et al., 2006). Based upon these safety data, a study using a higher dose of 1000 mg/day was initiated, with results reported in 2013 (Heresco-Levy et al., 2013). At the higher dose of 1000 mg/day, significant beneficial effects were observed in 13 subjects vs. placebo control with SSRI-nonresponsive depressive symptoms. The improvements were manifested within 2 weeks and persisted throughout the 6-week treatment period. These data suggest a  $>0.9$  effect size. In that study, a slow DCS titration was used, with 250 mg/day for 3 days, followed by 500 mg/day for 18 days (i.e., until the end of week 3); followed by 750 mg/day for 1 week (i.e., until the end of week 4), followed by 1000 mg/day (i.e., until the end of study). A statistically significant improvement was observed in the DCS group compared to placebo by the end of week 4, i.e., within 1 week of initiation of a DCS dose  $>500$  mg/day (see Figure 1).

[figure not shown]
